5. To estimate incidence rate ratios for venous and arterial thromboembolic events among patients with COVID-19 and different SARS-CoV-2 vaccine doses compared to the background population, using incidence rates estimated in objectives 1 to 3.

Study type: population-level cohort

Study population:

- 1) Pre-pandemic cohort to calculate background rates of venous and arterial thromboembolic events in the general population (year 2017-2019).
- 2) People with COVID-19 during the time when OMICRON was the dominant variant (coded or test positive). All participants are required to be visible in the data source since 1st January 2020 to have full records on infection and vaccination history.
- 3) People vaccinated against SARS-CoV-2 (+/- during the period when OMICRON was the dominant variant). All participants are required to be visible in the data source since 1st January 2020 to have full records on infection and vaccination history.

For all cohorts, individuals with recent VTE or ATE event (defined as having a diagnosis of VTE or ATE within 183 days prior to index date, with sensitivity analysis of using any time prior and 91-days as wash-out periods.) will be excluded.

	Phase II C3-001 – Study Protocol	
	Author(s): [name], [name]	Version: v3.1
		Dissemination level: public

Analysis:

Standardized incidence rate ratio (SIR) compared to the background population will be estimated using indirect standardization.

Cohorts will be stratified by prior COVID-19 infection occurrence and prior SARS-CoV-2 vaccination (COVID-19 and vaccine cohorts only), age, sex. All cohorts will additionally be stratified by whether patients are immunocompromised on the index date.

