deep vein thrombosis		No	Binary, time-to-event	[-183,-1]	IP,OP	SNOMED	n/a	All included cohorts	n/a	n/a
portal vein thrombosis		No	Binary, time-to-event	[-183,-1]	IP,OP	SNOMED	n/a	All included cohorts	n/a	n/a
splanchnic venous		No	Binary, time-to-event	[-183,-1]	IP,OP	SNOMED	n/a	All included cohorts	n/a	n/a

	Phase II C3-001 – Study Protocol	
	Author(s): [name], [name]	Version: v3.1
	Dissemination level: public	

thrombosis (SVT)										
cerebral venous sinus thrombosis		No	Binary, time-to-event	[-183,-1]	IP,OP	SNOMED	n/a	All included cohorts	n/a	n/a
acute myocardial infarction		No	Binary, time-to-event	[-183,-1]	IP,OP	SNOMED	n/a	All included cohorts	n/a	n/a
acute ischemic stroke		No	Binary, time-to-event	[-183,-1]	IP,OP	SNOMED	n/a	All included cohorts	n/a	n/a
stroke in general	stroke in general will include both ischemic, haemorrhagic and non-specifically recorded stroke.	No	Binary, time-to-event	[-183,-1]	IP,OP	SNOMED	n/a	All included cohorts	n/a	n/a

¹ IP = inpatient, OP = outpatient, ED = emergency department, OT = other, n/a = not applicable

² Specify whether a diagnosis code is required to be in the primary position (main reason for encounter)

8.6.3. Other covariates, including confounders, effect modifiers and other variables (where relevant)

Location at index date

For cohort 2 (Persons tested positive for SARS-CoV-2 or with a clinical diagnosis of COVID-19) and cohort 5 (Persons vaccinated against SARS-CoV2 infection) we will identify whether individuals were currently hospitalised on their index date. All people in the cohort 3 (Persons hospitalised with COVID-19) and cohort 4 (Persons requiring intensive services during a hospitalisation with COVID-19) will be hospitalised on their index date.

Demographics

Patients' age at index date and sex will be identified. Age groups will also be identified using the following groupings: <20; 20-44; 45-54; 55-64; 65-74; 75-84; ≥85 years. For those databases where such information is available, individual or area level socioeconomic status and whether they are living in the community or were a nursing home resident will also be identified.

Health conditions pre-index date

Individuals' history of the study outcomes will be identified over three time periods prior to the index date:

- 1) 30 days prior to one day prior index date,
- 2) 365 days prior to one day prior index date,
- 3) all available days observed up to one day prior to index date.

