8.7 Study size

For each database, all individuals that satisfy the eligibility criteria for a study cohort will be included.

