		Dissemination level: public

We will calculate crude incidence rate ratios (IRRs) for each event with 95% confidence intervals, for the vaccinated and COVID-19 cohorts compared against the background general population cohort. This will be done both overall and stratified by key factors including age, sex, prior COVID-19 diagnosis, prior vaccination status and whether patients are immunosuppressed. We will estimate the number of events expected among the vaccinated and COVID-19 cohorts using indirect standardisation by age and sex (with 10-year age bands), using the general population cohort as the standard population. We will calculate standardized incidence rate ratios (SIRs) and 95% confidence intervals comparing observed and expected rates. Rates will be reported overall, and by 10-year age bands, by sex, by prior COVID-19 diagnosis, by prior vaccination status and whether patients were immunosuppressed. A standardized incidence rate ratio above 1 will indicate that the observed rate for a specific outcome is higher than what is expected in the general background population.

Table 8: Primary, secondary, and subgroup analysis specification

A. Primary analysis

Hypothesis:	Objective 1 -3: Not applicable, descriptive incidence rate. Objective 4: use of intensive care services during a hospitalisation can be considered as key intermediate events between testing positive for SARS-COV-2 or having a clinical diagnosis of COVID-19 in an outpatient setting on the one end to a COVID-19-related death on the other. Objective 5: Covid-19 infection or vaccination may change the incidence rate of study events in population.
Exposure contrast:	Objective 1 -3: Not applicable, descriptive incidence rate. Objective 4: Not applicable, risk factor analysis Objective 5: Infected or vaccinated vs. the non-infected or non-vaccinated population
Outcome:	Objective 1 -3: Incidence rates of VTE, ATE Objective 4: VTE, ATE, death Objective 5: Incidence rates of VTE, ATE
Analytic software:	R

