	done both overall and stratified by key factors including age, sex, prior COVID-19 diagnosis, prior vaccination status and brand, and whether patients are immunosuppressed. We will estimate the number of events expected among the vaccinated and COVID-19 cohorts using indirect standardisation by age and sex (with 10-year age bands), using the general population cohort as the standard population. We will calculate standardized incidence rate ratios (SIRs) and 95% confidence intervals comparing observed and expected rates. Rates will be reported overall, and by 10-year age bands, by sex, by prior COVID-19 diagnosis, by prior vaccination status and brand, and whether patients were immunosuppressed. A standardized incidence rate ratio above 1 will indicate that the observed rate for a specific outcome is higher than what is expected in the general background population.
Confounding adjustment method	Name method and provide relevant details, e.g. bivariate, multivariable, propensity score matching (specify matching algorithm ratio and caliper), propensity score weighting (specify weight formula, trimming, truncation), propensity score stratification (specify strata definition), other.
	For incidence rates, we will estimate the rates with stratification. For incidence rate ration, standardized incidence rate ratio (SIRs) will be calculated.
Missing data methods	Name method and provide relevant details, e.g. missing indicators, complete case, last value carried forward, multiple imputation (specify model/variables), other.
	For cohort 2-5, we will only include individuals with complete exposure information.
Subgroup Analyses	List all subgroups
	All analysis will be stratified by age, sex, prior COVID-19 diagnosis, prior SARS-CoV-2 vaccination, whether patients were hospitalised or whether patients were immunocompromised on their index date will be reported, when sample size allowed.

B. Secondary Analysis 1

The only difference between the primary and secondary analysis is the outcomes of interest. Hence here we only show this item in the table.

Outcome:	1. Venous thromboembolic events
-----------------	---------------------------------

	Phase II C3-001 – Study Protocol	
	Author(s): [name], [name]	Version: v3.1
	Dissemination level: public	

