The included databases will vary in the data elements that they capture and in their current duration of follow-up. Depending on the dataset, not all study populations will be observed. For example, identifying the intensive services cohort will not be possible where inpatient hospital interventions are not observed. Similarly, not all outcomes may be available in all databases e.g. deaths. Some datasets may not capture COVID-19 diagnoses or tests occurring outside of hospital. Only the cohorts and outcomes that can reliably be identified will be assessed in the analyses. Since the vaccination programs changed over time (e.g. the primary vaccine courses targeted the general population, while the 4th dose were offered to more vulnerable people), the characteristics of patients receiving different doses may differ. However, we will stratify our analysis by prior vaccines whenever the power allows. It will also be assumed that vaccination recording is complete. Due to the availability of more recent data (CPRD is available until July 2022), some databases may have relative short follow-up time for study cohorts, and therefore may impact on the 90-days and 180-days incidence rates. The data elements that each data partner can provide will be detailed. The contextualisation of incidence rates using a historical background period assumes that coding practices and data recording are similar over time. However, this method has been used in previous studies focused on the 1st wave of covid, conducted by the same research group. [20,21] The analysis will calculate crude incidence rates and standardised incidence rates accounting for age and sex only. Differences in other potential confounders factors may exist and the characteristics of each cohort and stratification group will be inspected. No validation of outcomes using case note review will be performed.

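### Ten-year age bands for the SIR expected counts leave residual age confounding if a dose or brand cohort is skewed in age within a band; finer bands are a cheap remedy

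*Protocol*

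**What the plan says.** The abstract names the method without a band width: "Standardized incidence rate ratio (SIR) compared to the background population will be estimated using indirect standardization". The operative text is in section 8.8.5, repeated for objective 5 in Table 8: "indirect standardisation by age and sex (with 10-year age bands), using the general population cohort as the standard population". Section 11 describes the result as "standardised incidence rates accounting for age and sex only".

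Results are then cut finely. Table 8 says: "Rates will be reported overall, and by 10-year age bands, by sex, by prior COVID-19 diagnosis, by prior vaccination status and brand". Objective 5 concerns COVID-19 patients and "different SARS-CoV-2 vaccine doses compared to the background population, using incidence rates estimated in objectives 1 to 3", and section 8.6.1 defines vaccine exposure by dose and brand.

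On who received what, section 11 says that "the primary vaccine courses targeted the general population, while the 4th dose were offered to more vulnerable people". No age limit is given for any dose or brand.

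The demographics paragraph of section 8.6.3 lists a separate grouping for age: "<20; 20-44; 45-54; 55-64; 65-74; 75-84; ≥85 years". The cut points of the 10-year SIR bands are not stated.

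**The concern.** Indirect standardisation with one rate per band removes age confounding only if the exposed and background cohorts have the same age mix inside each band. Vaccination programmes that change by dose, as section 11 describes, give some reason to doubt this for dose and brand cohorts. The expected count would then reflect the average age of the band instead of the ages of the people vaccinated.

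Age is one of only two variables protecting this contrast, and the protocol reports SIRs at the cuts where a within-band shift is least likely to average out: a single band, a single brand, a single dose. Section 8.8.5 reads an SIR above 1 as a rate higher than expected in the background population. A shift in the expected count could therefore be read as an excess or a deficit, and two doses or brands with the same risk could appear to differ. A larger sample does not reduce this error.

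**Working it through.** The protocol states no SIR, expected count or age-specific rate, so there is no figure of its own to reproduce.

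**Inputs from the protocol:** 10-year age-by-sex bands with the general population cohort as standard (8.8.5, Table 8); age and sex only (section 11); reporting by band, brand and dose (Table 8, objective 5).

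**Inputs assumed:** the background rate is log-linear in age and is multiplied by g over 10 years, with g = 1.5, 2 or 2.5; the cohort covers only part of a band; ages are spread evenly; exposure has no effect.

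**One band.** At t years above the lower edge the rate is proportional to g^(t/10).

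- Mean over the band, which drives expected events: (g − 1)/ln g.
- Mean over the upper half, which drives observed events: (g − √g)/(½ ln g).
- Ratio for the upper half: 2√g/(1 + √g). Ratio for the lower half: 2/(1 + √g).

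For g = 2: 2 × 1.4142/2.4142 = 1.172, and 2/2.4142 = 0.828.

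| Rise per decade | SIR, upper half | SIR, lower half |
|---|---|---|
| 1.5 | 1.101 | 0.899 |
| 2.0 | 1.172 | 0.828 |
| 2.5 | 1.225 | 0.775 |

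Thinner slices give more. Under doubling, the top three years give 1.252 and the bottom three 0.770, with limits of 1.386 and 0.693 at the band edges. With a population that declines linearly after age 50, the half-band figures for ages 60 to 69 under doubling become 1.188 and 0.841.

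**Several bands.** The SIR is total observed over total expected; fully covered bands contribute no error. Take ages 55 to 70, even age spread, doubling (band mean 1/ln 2 = 1.443 times the rate at the lower edge).

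- Edges at 55, 65, 75 (rate at 55 set to 1). Ages 55–65: observed = expected = 10 × 1.443 = 14.43. Ages 65–70: expected 5 × 2 × 1.443 = 14.43, observed 14.43 × 0.828 = 11.95. SIR = 26.38/28.86 = 0.914.
- Edges at 50, 60, 70 (rate at 50 set to 1). Ages 55–60: expected 5 × 1.443 = 7.21, observed 7.21 × 1.172 = 8.45. Ages 60–70: both 28.85. SIR = 37.30/36.06 = 1.034.

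Other cohorts under doubling, with even or declining age density: ages 40–70 give 1.00 with edges at multiples of ten and 0.94–0.96 with edges at the fives; 60–70 give 1.00 and 0.94–0.97. Taking both sets of edges together, 65 and over gives 1.00–1.03, 80 and over 1.00–1.07, and 18 and over about 1.00. The largest multi-band error found at g = 2.5 is 0.875, for ages 55–70 with edges at the fives.

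**Five-year bands.** The rise over the band is now √g. For g = 2 it is 1.414, with square root 1.189: upper half 2 × 1.189/2.189 = 1.086, lower half 2/2.189 = 0.914. The error is about halved, and it vanishes when an age cut-off falls on a five-year edge.

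**The case against.** Ten-year age-by-sex bands are a conventional choice, and nothing here is contradictory or miscalculated. Section 11 discloses that only age and sex are accounted for, that recipients of different doses may differ, and that cohort and stratum characteristics will be inspected. Its remark about the fourth dose concerns vulnerability, which is not the same as an age cut inside a band, and finer age adjustment would not remove confounding by frailty. Both drivers of the size, the age gradient and the partial coverage of a band, come from outside the document. All of this stands and keeps the point minor.

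What remains is that the band width is an explicit choice in the protocol, that the finest reporting cuts are the most sensitive to it, and that neither disclosure nor stratifying by prior vaccination corrects age within a band.

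A reader might also set the half-band figures beside the confidence interval for a whole brand and conclude that the bias rivals sampling error. The documents do not support that comparison. A whole-brand SIR that spans several bands carries the smaller multi-band error, whereas a single-band SIR rests on fewer events and so has a wider interval.

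**Conclusion.** The point holds as a modest weakness in the analysis choice. Where a dose or brand cohort has a different age mix within a band from the background cohort, 10-year bands leave residual age confounding, in either direction. For a cohort confined to half a band, the band-specific SIR with no true effect is about 1.10 to 1.23 or 0.90 to 0.78, given an assumed 1.5- to 2.5-fold rise per decade. Overall SIRs across several bands move by about 0 to 9% under doubling, and by up to about 12.5% at 2.5-fold among the cohorts tried.

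Three stronger readings should be resisted:

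- That thrombosis rates double across a band is an assumption; the protocol has no age-specific rates.
- That a dose or brand SIR will be wrong by some fixed maximum, such as a quarter, does not follow. Thin slices can exceed that figure, most multi-band SIRs fall well below it, and no age limits by dose or brand are given.
- That the COVID-19 SIRs are affected to the same degree is not shown; the protocol gives no reason to expect infection to be age-targeted within a band.

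**What to change.** In section 8.8.5 and the objective 5 entry of Table 8, compute expected counts from background rates by sex and 5-year age band, and state the band edges. Alternatively, use single year of age with a Poisson model and an age spline, mainly for rare outcomes or small databases. Keep 10-year bands for display only.

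The cost is small. Age at index is already identified (8.6.3), and section 5 lists creation of the analytical code as still to be confirmed. Because objective 5 draws on the rates from objectives 1 to 3, the finer background rates must be produced in each database contributing an SIR. Indirect standardisation tolerates sparse exposed cells, so the drawback lies on the background side: slightly noisier rates for rare outcomes and smaller databases (IPCI has 1.39M active subjects in Table 1, against 5.8M in SIDIAP), or mild model dependence with a spline. The change does not address confounding by vulnerability, which should stay in the limitations.

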4. AMENDMENTS AND UPDATES

Number	Date	Section of study protocol	Amendment or update	Reason
V3.1	04/10/2023	Document history	Update	EUPAS register number added

	Phase II C3-001 – Study Protocol	
	Author(s): [name], [name]	Version: v3.1
	Dissemination level: public	

5. MILESTONES

Additional study specific deliverables (e.g. results of validation of new disease concepts, statistical analysis plan, etc.) might be requested but this will be on an individual basis

STUDY SPECIFIC DELIVERABLE	TIMELINE
Draft Study Protocol	June 2023
Final Study Protocol	July 2023
Creation of Analytical code	To be confirmed
Execution of Analytical Code on the data	To be confirmed
Interim Study Report (if applicable)	To be confirmed
Draft Study Report	To be confirmed
Final Study Report	To be confirmed

6. RATIONALE AND BACKGROUND

Coronavirus disease-2019 (COVID-19) patients are at increased risk of venous and arterial thromboembolic events. SARS-CoV-2 variants have evolved during the COVID-19 pandemic with the dominant variant being Omicron now (as of December 2021). Information relating to thromboembolic risk and its impact on COVID-19 largely relates to COVID-19 variants occurring earlier during the pandemic. Therefore, evidence used to contextualize coagulopathy risk in light of vaccination may now differ. Therefore, there is a need to better understand the risks of thromboembolic events among patients with COVID-19 associated with the Omicron variant, their impact on prognosis, and whether risk factors for such events remain the same, overall and in the context of prior COVID-19 infection, SARS-CoV-2 vaccination and among certain subgroups.

European Health Data Space

HealthData@EU pilot project is the European Health Data Space (EHDS) Pilot project that aims to investigate and establish an infrastructure and data ecosystem for the secondary use of health data for research, innovation and better policy making. The HealthData@EU pilot project will assess the ability to scale towards a Union-wide infrastructure as a core component of the European Health Data Space. The proposed study is one of the five use cases selected to test and inform HealthData@EU frameworks.

Occurrence of venous and arterial thromboembolic events among people with COVID-19

Coronavirus disease-2019 (COVID-19) may cause both venous and arterial thromboembolic events due to excessive inflammation, platelet activation, endothelial dysfunction, and stasis. [1] A number of observational studies and case series have reported high rates of venous and arterial thromboembolic events among patients hospitalised with COVID-19. In a case series of COVID-19 patients admitted to ICU in

	Phase II C3-001 – Study Protocol	
	Author(s): [name], [name]	Version: v3.1
		Dissemination level: public

the Netherlands, the incidence of thrombotic complications was found to be 31%, [2] while a similar case series from a hospital in Italy found the incidence of thromboembolic events to be 28%. [3] Meanwhile, the rate of venous thromboembolism was found to be as high as 69% for a case series from two French intensive care units (ICU).[4]

Studies assessing the incidence of thromboembolic events among people with COVID-19 during the early period of the pandemic were conducted in relatively small study populations, partly constrained by data availability at the time, and predominantly focused on hospitalised populations. Consequently, uncertainty remained around the incidence of thromboembolic events among patients with COVID-19. Several larger studies examining coagulopathy risk have since been conducted using routinely collected health data. One study from Sweden demonstrated an increased risk of deep vein thrombosis (DVT) up to 70 days post-COVID-19 diagnosis and an increased risk of pulmonary embolism up to 110 days post-COVID-19 diagnosis.[5] Meanwhile, another study from England reported an increased risk of venous thromboembolism up to 49 weeks post-COVID-19.[6] Studies have also observed that the elevated risk of thromboembolic events associated with COVID-19 infection may be attenuated following SARS-CoV-2 vaccination.[7] SARS-CoV-2 variants have changed over time, with Omicron now widely established as the dominant SARS-CoV-2 variant. On 26 November 2021, the European Centre for Disease Prevention and Control classified the Omicron B.1.1.529 variant as a variant of concern due to concerns regarding immune escape and potentially increased transmissibility compared to the SARS-CoV-2 delta variant.[8] However, existing studies largely examined COVID-19 during the period when Omicron was not the dominant variant. The risk of venous and arterial thromboembolic events with Omicron COVID-19 is therefore less well studied, particularly in the context of exposure to either prior COVID-19 infection or prior SARS-CoV-2 vaccinations.

Thromboembolic events and worsening of COVID-19 during the Omicron period

COVID-19 patients with thromboembolic events are at increased risk of worse outcomes, with a systematic review finding a strong association between cardiovascular and thromboembolic events and poor prognosis among people with COVID-19.[9] However, it has been suggested that the Omicron variant has a milder course and therefore, subsequent coagulopathy risk may differ. This may be further influenced by prior SARS-CoV-2 vaccination. As with measuring the incidence of thromboembolic events themselves, routinely collected data may also be used to describe the risks of worsening among people with COVID-19 during the period when Omicron was the dominant variant.

Risk factors for thromboembolic events among people with COVID-19 during the Omicron period

Various patient factors have been associated with worse outcomes among people with COVID-19 that occurred during the early stages of the pandemic when Omicron was not the dominant variant. Older age, male sex, hypertension, diabetes, and being overweight or obese have all been reported to be associated with an increased risk of hospitalisation and mortality among people with COVID-19.[10–16] Many of these same factors have also previously been seen to predispose individuals to thromboembolic events. [17,18] In one study a set of pre-existing cardiovascular risk factors were associated with increased mortality among people with COVID-19, independent of patients' age and sex. [19] Whilst the associations between such risk factors and thromboembolic events among patients with SARS-CoV-2 variants has been studied, this largely included data on COVID-19 during the early stages of the pandemic when Omicron was not the dominant variant. Information is limited on whether risk factors for venous and arterial thromboembolic events

	Phase II C3-001 – Study Protocol	
	Author(s): [name], [name]	Version: v3.1
	Dissemination level: public	

remain the same for COVID-19 associated with the Omicron variant, and to what degree this may be influenced by prior SARs-CoV-2 vaccination and the impact of immunosuppression.

Contextualising incidence rates for thromboembolic events with COVID-19 during the Omicron period

Two studies have compared incidence rates of thrombosis and thrombocytopenia after vaccination against SARS-CoV-2 and with COVID-19 using data from the United Kingdom and Spain. These studies calculated incidence rates of thromboembolic events in people vaccinated against SARS-CoV-2 and in people with COVID-19 infection and compared them to pre-pandemic rates in a historic background cohort.[20,21] Compared to pre-pandemic rates, standardised incidence ratios were elevated for venous thromboembolism shortly following both initial vaccination against SARS-CoV-2 and for COVID-19 infection, although to a much greater extent with COVID-19 infection. It is uncertain however to what extent evidence generated by these studies is generalisable to COVID-19 infection during the Omicron period.

